### **9.2.3 Growth**

Growth will be measured as height (velocity) and weight (Z-score) using a certified weight scale. BMI will be calculated by weight (kg) / height (m). Change will be defined as linear growth deficit (weight and BMI for age) compared to a standard growth curve (Z-score, SD from P50).

#### 9.2.4 Quality of Life Questionnaire (PedsQL)

Patients and caregivers will be asked to complete a QoL questionnaire (PedsQL) at Visit 3 and Visit 9. Details of the questions included on the questionnaire are provided in [Appendix 4](#).

#### 9.2.5 Biomarkers and PK Samples

Blood samples for autotaxin and p-C4 will be drawn at Visits 3, 4, and 9 only for children with body weight >10 kg. Blood for A4250 PK assessment will only be drawn at Visits 4 and 9 (only for children with body weight >10 kg), and as close to the onset of an SAE as possible, should an SAE occur. Samples will be processed and transported to a laboratory per instructions in the laboratory manual.

#### 9.2.6 PELD/MELD Score

At randomization and end of treatment, PELD score will be calculated for children up to 12 years of age. For children 13 years or older, the MELD score will be calculated.

PELD Score =  $4.80 * \ln(\text{total bilirubin}) + 18.57 * \ln(\text{INR}) - 6.87 * \ln(\text{albumin}) + 4.36$  (if patient <1 year: scores for patients listed for liver transplantation before the patient's first birthday continue to include the value assigned for age (<1 year) until the patient reaches the age of 24 months) + 6.67 (if the patient has growth failure [ $\leq 2$  SD])

Laboratory values less than 1.0 will be set to 1.0 for the calculation of the PELD score.

MELD Score =  $9.57 * \ln(\text{creatinine}) + 3.78 * \ln(\text{total bilirubin}) + 11.2 * \ln(\text{INR}) + 6.43$

Laboratory values less than 1.0 will be set to 1.0 and serum creatinine values greater than 4.0 mg/dL (equivalent to 353.6  $\mu\text{mol/L}$ ) will be set to 4.0 for calculation of the MELD score.

#### 9.2.7 Fibroscan®

Where available, Fibroscan® will be performed as per institution standard practice at Visits 3 and 9.

#### 9.2.8 Markers of Fibrosis

APRI score and Fib-4 score will be calculated at randomization and at end of treatment.

APRI =  $[(\text{AST in U/L}) / (\text{AST ULN in U/L})] / (\text{Platelets in } 10^9/\text{L})$

Fibrosis 4 Score =  $(\text{Age} * \text{AST in U/L}) / (\text{Platelets in } 10^9/\text{L} * \sqrt{(\text{ALT in U/L})})$ .

#### 9.2.9 Global Impression of Change and Global Impression of Symptom Measures

Patients ( $\geq 8$  years of age), caregivers, and clinicians will complete the PGIC and the PGIS measures ([Appendix 3](#)) at randomization (Visit 3; PGIS only), Visits 4 and 6, and at EOT (Visit 9).

The PGIC items assess change in itch (patient version), scratching (caregiver and clinician versions), and sleep (all versions) since starting the study drug. The PGIS items assess itch

(patient version), scratching (caregiver and clinician versions), and sleep (all versions) in the past week. Caregivers and clinicians will complete the PGIC and PGIS for all patients; those patients  $\geq 8$  years of age will complete the patient version.

## 10 ASSESSMENT OF SAFETY

The timing and frequency of safety assessments are described in [Section 7.1.3](#) and in [Table 1](#) above.

The primary safety analysis for this study will include the incidence of total treatment-emergent adverse events (TEAE) and TEAEs categorized by causality, severity, and seriousness assessments made by the investigator by comparing study drug exposure to placebo.

Trends in safety will also be evaluated for the following assessments:

- Physical examinations
- Concomitant medications
- Vital signs
- Laboratory test results (including clinical chemistry, hematology, urinalysis, AFP, and vitamins A and E, 25-hydroxy vitamin D, and INR)
- Abdominal ultrasound
- Discontinuations due to AEs

### 10.1 Adverse Events

#### 10.1.1 Definitions and Investigator Assessments

An AE is defined as any untoward medical occurrence in an enrolled patient regardless of causal relationship with study drug. An AE can therefore be any clinically significant unfavorable and unintended sign, symptom, or disease that occurs once a patient is enrolled (ICF is signed) in the study until the patient is discharged from the study, whether or not related to the study drug.

##### 10.1.1.1 Clinical Significance

Clinical significance is defined as any abnormal finding that results in further clinical investigation(s), treatment(s), or the diagnosis of new condition. Patient-reported events and protocol-mandated laboratory values, vital signs, and physical examination findings can be considered clinically significant (i.e., an AE) if there is a deterioration as compared to baseline. Examples of clinically significant worsening from baseline could include, but is not limited to, events causing withdrawal from the study and events requiring medical intervention outside of the study causing apparent clinical manifestations, or judged relevant by the investigator.

##### 10.1.1.2 Serious Adverse Events

Serious criteria are applied by the investigator to each AE as specifically defined below. These criteria are used to determine whether an AE is serious or non-serious. The assessment

is made independently of severity assessment (Section 10.1.1.3). For example, the development of a severe rash that occurs after signing of informed consent may not meet serious criteria as defined below and therefore would be considered a severe, non-serious AE.

Any AE that meets any 1 of the following 6 criteria is considered an SAE:

- The outcome of the AE is **death**
- The AE is immediately **life-threatening**. Life-threatening means that the patient is, in the opinion of the investigator, at immediate risk of death from the reaction as it occurred. This does not include an AE that, if more severe, might have caused death
- The AE results in persistent or significant **disability/incapacity**. Disability means a substantial disruption of a person's ability to conduct normal life functions
- The AE requires or prolongs **hospitalization**
- The AE results in a **congenital anomaly/birth defect**
- **The AE is an important medical event**. Important medical events may meet serious criteria should the investigator assess that they may significantly jeopardize the patient, represent a significant hazard, or requires medical/surgical intervention to prevent one of the outcomes listed above. Examples of potential SAEs based on this criteria include, but are not limited to, allergic bronchospasm requiring intensive treatment in an emergency room or at home, blood dyscrasias or convulsions even if they do not result in inpatient hospitalization, or the development of drug dependency and drug abuse.

#### 10.1.1.3 Severity Assessment

Severity assessments are based on the intensity of the event in relation to expectation. The investigator will assess the intensity of AEs based on the following definitions:

- Mild (awareness of sign or symptom, but easily tolerated)
- Moderate (discomfort sufficient to cause interference with normal activities)
- Severe (incapacitating, with inability to perform normal activities)

Severity is a measure of intensity where seriousness is defined by the criteria outlined in [Section 10.1.1.2](#). An AE of severe intensity need not necessarily be considered serious. For example, nausea that persists for several hours may be considered severe nausea, but not meet serious criteria, and therefore would be assessed as a severe AE but not an SAE.

#### 10.1.1.4 Causality Assessment

The investigator determines the causality of all AEs to the study drug using medical judgment and considering all relevant factors such as (but not limited to) the underlying study indication, coexisting disease, concomitant medication, relevant history, pattern of the AE, temporal relationship to the study drug, and de-challenge or re-challenge. The causality assessment of the AE/SAE is to be made as follows.

### **Related to study drug (possibly, probably, or definitely related)**

Based on medical judgment, there is at least a reasonable possibility that the study drug caused the event; one or more of the following criteria apply:

- The event follows a reasonable temporal sequence from administration of study drug
- The event could not be reasonably attributed to the known characteristics of the patient's clinical state, environmental or toxic factors, or other modes of therapy administered to the patient
- The event follows a known pattern of response to study drug
- The event disappears or decreases on cessation or reduction in dose of the study drug. (It should be noted that in some situations an AE will not disappear or decrease in intensity upon discontinuation of study drug despite other clear indications of relatedness)
- The event reappears or worsens when the study drug is re-administered

### **Unrelated to study drug (unlikely or unrelated)**

Based on medical judgment there is no reasonable possibility that the study drug caused the event; one or more of the following criteria apply:

- The event does not follow a reasonable temporal sequence from administration of study drug
- The event could be reasonably attributed to the known characteristics of the patient's clinical state, concurrent illness, environment or toxic factors, or other modes of therapy administered to the patient
- The event does not follow a known pattern of response to study drug
- The event does not disappear or decrease on cessation or reduction in dose of the study drug, and it does not reappear or worsen when the study drug is re-administered

#### **10.1.2 Recording of Adverse Events**

It is the investigator's responsibility to assess whether each untoward event is a clinically significant worsening from baseline, thereby considered an AE. For all AEs, the severity, seriousness, and causality to study drug for each AE as outlined in [Section 10.1.1](#) will be assessed and recorded in the eCRF.

All serious and non-serious AEs are collected once the caregiver/patient has signed the ICF and until the post-treatment follow-up (Visit 10) or 28 days after the last dose of study drug.

Any AEs or SAEs that are unresolved at the patient's last AE assessment in the study are followed up by the investigator until resolution or stabilization up to the database lock and recorded in the eCRF. Albireo retains the right to request additional information for any patient with ongoing AE(s) or SAE(s) at the end of the study.

TEAEs are defined as any AE that occurs after randomization (Day 0). All AEs that occur in the Screening Period, i.e., after enrollment and prior to randomization, will be collected on the eCRF as non-treatment-emergent AEs.

If there is a clinically significant deterioration of a laboratory value/vital sign or other routine study assessment that is associated with a diagnosis, the clinical diagnosis will be reported as an AE and the associated signs and symptoms will be considered additional information unless the sign or symptom is more severe than expected given the diagnosis. For example, if an investigator diagnoses a study patient with hepatitis during the study period, hepatitis would be considered the AE and the concomitant signs and symptoms of abdominal pain, vomiting, and elevated ALT and AST would not be reported separately unless, in the opinion of the investigator, one of these signs or symptoms is more severe than expected and therefore a separate AE assessment is indicated.

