### **7.1.3.2 Treatment Period (Day 0 to Day 168)**

#### **Study Day 0/Clinic Visit 3 (Randomization)**

At the randomization visit, the following assessments will be conducted:

- Review inclusion/exclusion criteria ([Section 7.2](#))
- Review concomitant medications, medical and surgical history
- Physical examination, including voluntary photography ([Section 10.2.5](#))
- Skin examination ([Section 10.2.5](#))
- Vital signs ([Section 10.2.6](#))
- Albireo PRO/ObsRO eDiary review for compliance and entrance criteria requirement (see Inclusion Criteria 4, [Section 7.2.1](#))
- Clinical chemistry and hematology ([Section 10.2.1](#))
- s-BA ([Section 9.2.1](#))
- Autotaxin and p-C4 (samples will not be taken for patients  $\leq 10$  kg)
- 25-hydroxy vitamin D
- Alfa-fetoprotein (AFP)
- Abdominal ultrasound ([Section 10.2.7](#))
- Fibroscan®, where available ([Section 9.2.7](#))
- Administer QoL (Pediatric Quality of Life Inventory [PedsQL]) questionnaire
- Patient/caregiver/clinician complete the patient global impression of symptoms (PGIS)
- Urine pregnancy test for girls who have reached menarche
- AE monitoring
- Study drug is dispensed and patients are instructed to administer daily from Day 1

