### **7.2.3 Withdrawal of Patients**

Patients/caregivers will be informed that they have the right to withdraw from the study at any time, without prejudice to their medical care, and that they are not obliged to state their reasons.

Any withdrawal, and reasons for withdrawal, must be fully documented in the electronic case report form (eCRF) and source documents and the patient followed by the investigator/investigative staff. Even after the study is completed at the Follow-up Visit, the investigator/investigative staff will, regardless of reason for withdrawal, record any patient data they receive concerning SAEs, and all drug-related non-serious AEs, and subsequently report these according to Section 10.1. Withdrawn patients will not be replaced.

Patients will be withdrawn in the following circumstances:

- A patient's/caregiver's desire for withdrawal for any reason
- Lost to follow-up (every effort must be made to contact the patient/caregiver; a certified letter must be sent)
- An AE that, in the opinion of the investigator, necessitates withdrawal
- A worsening of the symptoms related to diarrhea occurs
- Death
- Patient/caregiver estimation of intolerable symptoms
- A patient's/caregiver's substantial noncompliance (eDiary and study drug compliance) or protocol violation

- An investigator's opinion that continuing the patient in the study is not appropriate. The investigator may withdraw a patient at any time, if it is considered to be in the patient's best interest

A patient who prematurely withdraws due to intolerable symptoms and has completed at least 12 weeks treatment in the double-blind study, will be offered the opportunity to enter open-label Study A4250-008. A patient who withdraws from treatment prematurely and does not enter Study A4250-008 will have EOT (Visit 9) assessments at the time of withdrawal and a follow-up assessment (Visit 10) 28 days following the last dose of study drug, and the patient will be recorded as withdrawn.

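### The TEAE definition has no worsening clause, so an adverse event that begins in Screening and worsens on study drug can be left out of the primary safety tables, depending on how the site records it

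*Protocol*

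**What the plan says.** Protocol Section 10.1.2 sets the classification in two consecutive sentences. The first is "TEAEs are defined as any AE that occurs after randomization (Day 0"). The second is "All AEs that occur in the Screening Period, i.e., after enrollment and prior to randomization, will be collected on the eCRF as non-treatment-emergent AEs". The wording is the same in the versions dated 29 April 2019 and 24 June 2019.

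The same section asks the investigator to judge "whether each untoward event is a clinically significant worsening from baseline, thereby considered an AE". Section 10.1.1.1 adds that patient-reported events and protocol-mandated findings "can be considered clinically significant (i.e., an AE) if there is a deterioration as compared to baseline".

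Section 10 states: "The primary safety analysis for this study will include the incidence of total treatment-emergent adverse events (TEAE"), broken down by causality, severity and seriousness. In Section 11.2.2.7 the tables for intensity, drug-relatedness, study discontinuation and serious events are all restricted to TEAEs.

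On timing, randomization is on Day 0, and the Visit 3 list reads: "Study drug is dispensed and patients are instructed to administer daily from Day 1".

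**The concern.** A treatment-emergent definition is meant to capture what changes once drug is taken. That includes new events and existing events that get worse. The rule here names only the first kind, and it tells sites to file Screening events under the opposite label.

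The gap could matter in this trial. Screening lasts 35 to 56 days, so an event that begins in Screening may still be running at the first dose. Exclusion criterion 4 bars diarrhea only when it is chronic and needs intravenous fluid or nutritional intervention, so a child with milder diarrhea can be randomized. Section 5.3.1 expects loose stools or diarrhea from the drug's mechanism. Section 7.2.3 lists among its reasons for withdrawal: "A worsening of the symptoms related to diarrhea occurs". A child could be withdrawn because diarrhea that began in Screening became worse on treatment, and still be absent from the table of TEAEs leading to discontinuation.

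At stake is whether the primary safety tables count on-drug worsening in the same way at every site.

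**Working it through.** No alpha, power or rate enters this point. The check sets the rules side by side, applies them to four kinds of event, and then sizes one misclassified child.

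**Step 1. Apply the rules.**

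| Event | Rule that applies | Classification |
|---|---|---|
| New event after the first dose | 10.1.2, first sentence | TEAE |
| Sign present before consent, worse on drug | The sign is medical history (10.2.3); an AE arises only after consent (10.1.1), so the worsening is the first AE, after Day 0 | TEAE |
| Event new in Screening, continuing, worse on drug | One continuing record: 10.1.2, second sentence | Not a TEAE |
| Same event | Worsening entered as a new AE: 10.1.1.1 and 10.1.2 | TEAE |
| Event after randomization, before first dose | 10.1.2, first sentence | TEAE, with no drug taken |

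The third and fourth rows are the same clinical course with opposite labels.

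**Step 2. Does the text choose between those two rows?** The worsening language in 10.1.1.1 and 10.1.2 settles whether an untoward event is an AE at all. It does not say that an AE already on record receives a second record when it worsens, and 10.1.1.1 is permissive. Baseline is not defined for adverse events. The default in 11.2.2.1 (last assessment before first intake) is written for a parameter, and 10.1.2 applies its worsening test to events collected from consent onward, before that baseline exists. The text allows either row and requires neither.

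**Step 3. Size of one misclassified child.** Section 11.1 plans at least 20 evaluable children per arm and 60 to 70 enrolled.

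- At 20 per arm: 1/20 = 5.0 percentage points.
- At 70/3 = 23.3 per arm: 1/23.3 = 4.3 percentage points.

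This applies to the rows that the event would have entered (preferred term, intensity, discontinuation). In the any-TEAE row the child is missed only if there is no other TEAE.

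**Step 4. Direction.** Let w_A and w_P be the proportions with an on-drug worsening of a Screening event on active drug and placebo, and q the share of these entered as new events. Sites are blinded, so take q as equal across arms. The tables then show q·w_A − q·w_P = q(w_A − w_P). With q between 0 and 1, a true excess on active drug shrinks and none is created. The documents give no value for q, w_A or w_P.

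**Step 5. Start of window.** Randomization is on Day 0 and the first dose on Day 1, so the pre-dose stretch inside the window is planned to be about one day.

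**The case against.** The strongest reply is that nothing is lost. Section 10.1.2 makes worsening from baseline the test for an AE, and 10.1.1.1 gives events causing withdrawal as an example of it. A worsening on drug is then an AE in its own right, it occurs after Day 0, and so it is a TEAE. This is a fair reading and many sites may follow it. It shows that the text does not force the loss. It does not show that the text prevents it, because no sentence calls for a second record.

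Several limits on the consequence also stand:

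- Signs that the child had before consent are medical history, so their worsening already counts. Only events that arise within Screening, persist and then worsen are exposed.
- Liver enzyme rises appear in the laboratory summaries whatever their TEAE status.
- Section 10 lists discontinuations due to AEs without restricting them to TEAEs, and Section 11.2.2.4 tabulates withdrawal reasons.
- SAE reporting from consent, the patient listings and the DSMB's unblinded review are unaffected.

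It can also be said that TEAE flags belong in a statistical analysis plan, which is not shown. That plan could restate the definition. But the protocol states its own rule and adds a collection instruction, and a later plan cannot recover the date and grade of a worsening if the eCRF did not capture them separately.

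On the Day 0 point, the gap is short and the same in every blinded arm. The protocol does not say whether Visit 3 fasting and blood draws come before or after randomization, so they may lie outside the window already.

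**Conclusion.** The point holds as an ambiguity in a stated rule that feeds the primary safety analysis. The protocol lets two compliant sites classify the same on-drug worsening in opposite ways, and one of those ways removes it from the TEAE tables. It should be corrected.

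A reader might infer that every such event is filed as non-treatment-emergent and disappears. The documents do not support that, because entering the worsening as a new AE is also allowed. A reader might also want a count of events lost. The protocol gives neither the frequency of Screening events ongoing at first dose nor the frequency of worsening, so the number is unknown and may be zero. What can be said is the weight of each case: 5 percentage points in the affected row of that arm, assuming about 20 children per arm.

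The start of the window at randomization instead of first dose is a minor defect.

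**What to change.** In Section 10.1.2, define a TEAE as an adverse event with onset on or after the first dose of study drug, or with onset before the first dose that increases in severity or becomes serious on or after the first dose. In the eCRF instructions, have sites record such a worsening with its own date and grade, so that the flag can be derived the same way everywhere. The first clause also moves the start of the window from randomization to first dose.

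The cost is one sentence and one instruction. Reported TEAE counts may rise slightly. No clinical rule changes.

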### **10.1.3 Recording and Reporting of Serious Adverse Events**

Every SAE (regardless of severity and causality) that occurs once the caregiver/patient has signed the ICF and until the post-treatment follow-up (Visit 10), and 28 days after the final dose of study drug, should immediately and not later than within 24 hours of knowledge of the event, be reported by the investigator or delegate in the SAE report form.

Report of a SAE must include at least the following information:

- Patient identification information (study number, site number, initials, and date of birth [as per local country requirements for data protection])
- The last study drug administration date
- The diagnosis of the event with the description (or a brief description of signs/symptoms/clinical course if the diagnosis is not available) and the date of onset
- The action used to treat the event (i.e., treatment medications, temporary discontinuation)
- The reason(s) for considering the event serious
- The relationship of the event to the study drug or to the study procedure (e.g., the investigator's assessment of causality)
- A brief narrative of the SAE

Follow-up reports including all new information obtained of the subsequent course of the SAE must be prepared and the information collected in the SAE submitted to [REDACTED] (Pharmacovigilance and Safety Services Department) by e-mail within 24 hours of knowledge of the event.

The pharmacovigilance manager (PVM) may contact the investigator to obtain further information on a reported SAE. The investigator/investigative staff must respond to any

request for follow-up information or answers to questions regarding the SAE within the same timelines as for initial reports.

The PVM reports the occurrence of the SAE and follow-up to the Albireo medical monitor for medical assessment of the case.

Should an outcome of death occur within the study period or within 28 days after the last administration of study drug, an SAE form should be completed including the main and contributory causes of death.

All SAE reports must be e-mailed to the following e-mail address within **24 hours**:

[REDACTED]

[REDACTED]

If email is unavailable, SAEs may be transmitted via fax to the following number:

[REDACTED]

In a study-related medical emergency situation, when the assigned medical monitors for the study cannot be reached by a caller, an on call physician can be reached 24 hours per day, 7 days per week, via the [REDACTED] call center. The following number is a chargeable telephone number allowing a global reach from both landlines and mobile phones and the internet page indicated below contains a list of country-specific toll-free telephone numbers that is provided. It should be noted that not all countries globally have access to toll-free numbers as indicated on the “24/7 Medical Help desk” index. Countries without toll-free numbers need to dial the chargeable number as indicated below. Furthermore, toll-free numbers might not be available from mobile phones.

[REDACTED]

[REDACTED]

